8.1.2. Sensitivity Analyses

In case at least one of the two primary comparisons is statistically significant, a sensitivity analysis will be conducted (on the statistically significant comparison(s)).

The following sensitivity analyses are defined to assess the robustness of results on the primary endpoint versus assumptions used in the statistical model for the main estimators. Before applying the analyses described below, when applicable, any datapoint collected in the week after intake of prohibited medications will be set to missing (applying the hypothetical strategy for ICEs defined in [Section 3.3.1](#)).

- The comparison between treatment and control will be performed in the FAS population by means of MI under missing at random (MAR) instead of MNAR assumption. The MI approach described in [Section 8.1.1](#) will then be repeated by changing Step 1 MNAR assumption to MAR assumption. Treatment and SANDE Global Score at baseline, Week 4 and Week 8 will be used in the FCS method. The seeds will remain the same.
- Tipping point will assess how departures from MI under MNAR assumptions must be in order to overturn conclusions from the primary superiority analysis. Tipping point will be based on iterative application of MI approach described in [Section 8.1.1](#), where the imputed values for each rhNGF arms are shifted at a constant Δ to represent a worse effect in each iteration. The tipping points are the smallest Δ s at which no statistical significance is shown (one-sided $p \geq 0.0125$) for each arm. Tipping point analysis will be run only if the superiority has been proven for at least one of the CCI of the rhNGF. The tipping point will be firstly searched in the values defined by \pm SD of the SANDE Global Score observed at baseline in the overall sample. If not found, the range will be enlarged to ± 2 SD.
- Analysis on complete cases not having taken prohibited medications in the week before assessment. Patients in FAS without any missing SANDE global score (i.e. evaluable at Baseline, Week 4 and Week 8) will be fitted into MMRM model described in [Section 8.1.1](#).

The following additional sensitivity analyses will be performed:

- Analysis on all observed cases. Patients with missing primary endpoint (i.e. change from Baseline at Week 8 missing) will be excluded. All observed data will be fitted into MMRM model described in [Section 8.1.1](#).
- MMRM described in [Section 8.1.1](#) will be applied to Per-Protocol Set based on the same imputed dataset described in [Section 8.1.1](#).

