10.6.3 Sensitivity and Supportive Analyses

In case at least one of the two primary comparisons is statistically significant, a sensitivity analysis will be conducted (on the statistically significant comparison(s)).

The following sensitivity analyses are defined to assess the robustness of results on the primary endpoint versus assumptions used in the statistical model for the main estimators. They will be done after having applied the hypothetical strategy for ICEs, when expected (i.e., after having set to missing the observed values collected in the week after the use of a prohibited medication):

- The comparison between treatment and control will be performed in the FAS population by means of MI under the missing at random (MAR) instead of the MNAR assumption.
- A tipping point strategy will be used as a sensitivity analysis for missing data for assessment of superiority (if shown) of rhNGF. Tipping point will assess how departures from MI under MNAR assumptions must be in order to overturn conclusions from the primary superiority analysis. Tipping point will be based on iterative application of MI described in § 10.6.2, where the imputed values for each rhNGF arms are shifted at a constant Δ to represent a worse effect in each iteration. The tipping points are the smallest Δ s at which no statistical significance is shown (one-sided $p \geq 0.0125$) for each arm. Tipping point analysis will be run only if the superiority has been proven for at least one of the two concentrations of the rhNGF. The tipping point will be firstly searched in the values defined by $\pm SD$. If not found, the range will be enlarged to $\pm 2SD$.
- Analysis on complete cases only (i.e., without considering patients with missing primary endpoint for any reason and after having discarded any observed case after the ICEs under the hypothetical strategy).
- Analysis on all observed cases (i.e., without considering patients with missing primary

endpoint for any reason and including data discarded due to ICEs handled under the hypothetical strategy).

- Analysis on the PP set instead of FAS.

Moreover, the following two supportive analyses by changing the strategies used in the primary estimand (therefore changing the estimand) will be done:

- Modified strategy #1 to handle ICEs for primary estimand:

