4.4. Analysis Window/Visit

For safety and efficacy endpoints, data will be evaluated and reported according to the nominal visit at which they have been collected, even if performed out of the tolerance interval limits declared in [Figure 1](#).

Efficacy analyses. Before applying any imputation methods, or any other strategy required by the handling of intercurrent events as detailed in [Section 3.3](#), a remapping will be done for any missing assessment at each planned visit. Remapping is allowed only for missing total scores (i.e. missing data for each item will not be replaced). In case data are missing at a given nominal visit, data collected at any other unscheduled visit (or ETV if done within an acceptable time-window of a previous visit) will be remapped to that visit, if the date of collection is within the tolerance interval limits defined in table of activities in [Section 13.1](#) (i.e. ± 1 for V3 – Day 13, ± 1 for V4 – Day 28, ± 2 for V5 – Day 56). Data collected under a nominal visit at out of tolerance interval limits will be used in the analysis unless the patient is declared an early study withdrawal: in this latter case, the evaluations recorded under the nominal visit will be set to missing and the actual values will be moved to a new timepoint named “Early Termination Visit”. This new timepoint will be only listed.

Safety analyses. Data collected under a nominal visit at out of tolerance interval limits will be treated as described for the efficacy. Data collected at an “Early Termination Visit” will be tabulated, separately from nominal visit values (i.e. Week 4 and Week 8).

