8.1.1. Primary Analysis

The overall null hypothesis H_0 is that the change from baseline in the SANDE Global Score for both of the two concentrations of rhNGF ophthalmic solution (μ_{DOSE5} and μ_{DOSE10}) are greater or equal (worse and no improvement, respectively) than the vehicle one ($\mu_{VEHICLE}$):

$$H_0 = \mu_{DOSE5} \geq \mu_{VEHICLE} \text{ and } \mu_{DOSE10} \geq \mu_{VEHICLE}$$

$$H_1 = \mu_{DOSE5} < \mu_{VEHICLE} \text{ or } \mu_{DOSE10} < \mu_{VEHICLE}$$

where μ denotes the mean change from baseline at week 8 in SANDE global score. For SANDE global Score, lower score is better.

Considering the multiple comparisons (rhNGF 5 mcg/mL versus vehicle, and rhNGF 10 mcg/mL versus vehicle) to claim overall superiority, a Bonferroni multiplicity correction of type I error will be applied on multiple comparisons. Each comparison will be consequently tested at one-sided alpha = 0.0125, in order to preserve the overall one-sided alpha of 0.025. The overall null hypothesis H_0 will be rejected if the associated primary analysis one-sided p-value will be lower than 0.0125 for one of two comparisons or both comparisons.

The primary analysis will be performed via Mixed-effects Model for Repeated Measures (MMRM) in the FAS according to the planned treatment. The analyses will include the change from baseline in SANDE global score as the dependent variable; the fixed effects of treatment (3 levels: rhNGF 5 mcg/mL, rhNGF 10 mcg/mL, and vehicle), visit (2 levels: Week 4, Week 8), baseline value, and treatment by visit interaction. An “unstructured” covariance matrix will be used. If the model fails to converge by using unstructured covariance matrix, compound symmetry matrix will be used instead. Each treatment group (IMP1 and IMP2) will be compared with the vehicle group at Week 8 using the difference in least square means (LS means) (i.e. difference between each concentration group and vehicle in mean change from baseline). The model can be summarized as follows:

$$\text{change from baseline} = \beta_0 + \beta_1 \text{treatment} + \beta_2 \text{base} + \beta_3 \text{visit} + \beta_4 \text{treatment} * \text{visit} + \varepsilon$$

where $\varepsilon \sim N(0, R)$ and R is the “unstructured” covariance matrix with blocks defined by the patients.

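### The all-observed-cases MMRM in SAP 8.1.2 excludes every patient without a Week 8 score, so it discards observed Week 4 scores and is in fact a Week 8 completers' analysis

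*SAP*

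**What the plan says.** The primary model (SAP 8.1.1) is an MMRM on change from baseline in SANDE Global Score, with fixed effects of treatment, "visit (2 levels: Week 4, Week 8), baseline value, and treatment by visit interaction", and an unstructured covariance.

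Among the additional sensitivity analyses, SAP 8.1.2 lists one on all observed cases. Two of its instructions pull against each other:

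- One sets the exclusion: "Patients with missing primary endpoint (i.e. change from Baseline at Week 8 missing) will be excluded".
- The next sentence, which points back to the primary model, begins "All observed data will be fitted into MMRM model described in".

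Protocol 10.6.3 gives the same restriction, whatever the cause of the missing value; its entry begins "Analysis on all observed cases (i.e., without considering patients with missing primary". It adds that values discarded under the hypothetical strategy for prohibited medication are kept. The exclusion is thus in both documents and is not a transcription slip.

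Three neighbouring provisions matter:

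- The complete-case analysis in SAP 8.1.2 uses "Patients in FAS without any missing SANDE global score (i.e. evaluable at Baseline, Week 4 and Week 8"), after removing scores taken in the week after prohibited medication.
- The analysis by multiple imputation under missing at random (MAR) states that "Treatment and SANDE Global Score at baseline, Week 4 and Week 8 will be used in the FCS method".
- For an early study withdrawal with an out-of-window visit, SAP 4.4 says that for efficacy "the evaluations recorded under the nominal visit will be set to missing". The value moves to an early-termination timepoint that is only listed.

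**The concern.** The reason to fit a two-visit MMRM without imputation is that a patient seen at Week 4 but not at Week 8 still informs the Week 8 estimate through the within-patient correlation. That makes the estimate valid when missingness depends on the Week 4 score. The exclusion removes exactly those patients. The name and the instruction to fit all observed data tell the reader one thing, and the exclusion does another.

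The pattern can be expected. A patient who leaves between Visits 4 and 5 has a Week 4 score. The early exit assessment recorded as Visit 5 is set to missing if it falls outside the window.

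This is also the only legible inferential analysis of the primary endpoint that keeps scores taken after prohibited medication:

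- The MAR imputation, tipping-point and complete-case analyses set them to missing.
- The per-protocol analysis reuses the primary imputed data.
- The two modified strategies in SAP 8.1.3 discard or replace them.

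If this result differs from the primary one, the cause could be the handling of prohibited medication, the restriction to Week 8 completers, or both. SAP 8.1.1 places the sensitivity results beside the main result in a forest plot, where they will be read as evidence of robustness.

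**Working it through.** **Inputs from the documents.** Protocol 10.1 gives mean changes (SD) of -28.2 (26.36) on active and -17.4 (20.29) on vehicle, 92 evaluable patients per group, 5% not evaluable and 80% power. SAP 8.1.1 gives the test level: "Each comparison will be consequently tested at one-sided alpha = 0.0125".

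**The plan's own figure first.**

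- Difference: 28.2 - 17.4 = 10.8.
- n per group = (2.241 + 0.842)² × (26.36² + 20.29²) / 10.8² = 9.505 × 1106.5 / 116.64 = 90.2, so 91 against the stated 92.
- At 92 per group, power is 80.9% (normal) or 80.2% (unequal-variance t).
- 92 / 0.95 = 96.8, so 97 per group and 291 in total.

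The sample size reproduces, so the plan's means and SDs are a sound base for the check.

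**Who is used.**

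| Baseline | Week 4 | Week 8 | All observed cases, as written | MMRM without the exclusion | Complete cases |
|---|---|---|---|---|---|
| yes | yes | yes | in | in | in |
| yes | yes | no | **out** | in | out |
| yes | no | yes | in | in | out |

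As written, the analysis differs from the complete-case one only in keeping patients who miss Week 4 alone and in keeping scores after prohibited medication.

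**When the difference is biased.** Let d be the shift in an arm's mean Week 4 change caused by keeping only patients who have Week 8. With a linear Week 4 to Week 8 relation and the same SD at both visits, that arm's completer mean at Week 8 shifts by r × d, where r is the correlation. The bias in the treatment difference is r × (d active - d vehicle). It vanishes when the two shifts are equal. It appears when dropout rate, mechanism, Week 4 distribution or SD makes them differ.

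**Size with the plan's SDs.** Assumptions that are not in the documents: r = 0.7, dropout after Visit 4 logistic in the Week 4 change (slope 0.7 to 1.2 per 18 points), and the loss rates other than 5%. There were 400,000 simulated patients per arm, with a true difference of 10.8.

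| Loss, active / vehicle | Week 8 completers | Bias | Week 4 data kept |
|---|---|---|---|
| 5% / 5% | 11.1 to 11.3 | +0.3 to +0.5 | within about 0.1 of 10.8 |
| 10% / 5% | 11.9 to 12.5 | +1.1 to +1.7 | within about 0.1 of 10.8 |

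At equal 5% loss the remaining bias comes from the unequal SDs. With r = 0.5, the 10% / 5% bias is about 0.8 to 1.2. When vehicle loses more (5% / 15%), completers give about 9.8 to 10.3, an understatement.

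**Check of the cancelling condition.** Separate runs of the full two-visit MMRM used equal SDs, no Week 4 effect and one dropout mechanism for both arms. The bias was within about 0.1 at 5%, 10% and 20% loss.

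**Scale.** The unadjusted standard error of the difference at 92 per group is √(1106.5 / 92) = 3.47. So 0.3 to 0.5 points is 0.09 to 0.14 SE, and 1.1 to 1.7 points is 0.32 to 0.49 SE.

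**The case against.** **Already covered by other analyses.** MAR imputation uses the Week 4 scores, the primary copy-reference imputation keeps them, and a tipping-point analysis addresses departures from the primary assumption. This stands for the primary conclusion. It does not replace the present analysis, because each of those removes scores after prohibited medication.

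**Deliberate, and paired with the complete-case analysis.** Both documents state the exclusion, and Protocol Section 13 attributes the revised sensitivity section to a regulator's request. The log does not say that the exclusion itself was requested. The pairing is real but partial: comparing the two analyses largely isolates prohibited-medication handling among patients who have Week 8. It says nothing about the patients left out.

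**Eye pain as the cause of unequal dropout.** A reader might infer that tolerability will drive unequal loss in the follow-up period. The documents give little support. Study drug stops at Visit 4 and all arms then receive the same artificial tears. Patients who stop treatment for adverse events are asked to complete the assessments (Protocol 7.1.1). Those who leave the study before Visit 4 will often have no usable Week 4 score under SAP 4.4, so removing the exclusion recovers nothing for them. The 10% / 5% scenario is an illustration, not a forecast.

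**Small, and no decision rests on it.** At the only loss figure in the plan, the bias is about 0.1 SE. Superiority is declared from the primary Week 8 p-values, and SAP 8.1.2 opens by tying sensitivity analysis to comparisons that are already significant. Both points stand.

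**Conclusion.** The point holds for this one robustness check. The analysis is labelled and described as using all observed data but is a Week 8 completers' analysis. The bias sizes of 0.3 to 0.5 and 1.1 to 1.7 points rest on the assumed correlation, dropout model and, for the larger figure, unequal loss. Direction depends on which arm loses more.

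Three stronger readings should be resisted:

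- Dependence of dropout on the Week 4 score alone does not bias the treatment difference. It biases each arm's mean, and the difference only if the selection is unequal.
- The primary result and its error rate are not affected.
- The analysis is not an exact duplicate of the complete-case one, since it keeps patients who miss only Week 4 and scores after prohibited medication.

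The change is worth making because it is nearly free and makes the analysis do what its name says. It is not a condition for the trial's conclusion.

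**What to change.** In SAP 8.1.2, delete the sentence that excludes patients with a missing Week 8 change. State instead that the analysis:

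- includes every FAS patient with a baseline and at least one post-baseline SANDE Global Score (Week 4 or Week 8);
- keeps values taken after prohibited medication;
- fits the MMRM of Section 8.1.1 without imputation.

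Leave the complete-case analysis as it is. Record the departure from Protocol 10.6.3 in SAP Section 11. SAP Section 1 makes the SAP govern where the two documents differ on planned analyses.

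The cost is one replaced sentence and one entry in Section 11, with no new data. The downside is that the analysis is no longer matched to the complete-case one. The MAR imputation analysis then becomes the natural comparator for the effect of prohibited-medication handling, and the SAP could say so.

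If the exclusion is kept, the minimum is to rename the analysis as one of Week 8 completers and to state what it assumes about missingness.

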8.1.3. Supportive Analyses

Moreover, the following two supportive analyses by changing the strategies used in the primary estimand (therefore changing the estimand) will be done:

- Modified Strategy #1 to handle ICEs for primary endpoint will be modified as below:
 - Treatment discontinuation: a treatment policy strategy will be applied where all the observed values will be used regardless of the occurrence of the ICEs. Missing data due to any reason will be handled by using a multiple imputation with a copy-reference approach (see [Section 8.1.1](#)).
 - Use of a pre-defined prohibited medication at any time during the study: a hypothetical strategy will be applied where any data collected after the first administration of a prohibited medication will be set to missing. Missing data will

be imputed by using a multiple imputation with copy-reference approach (see [Section 8.1.1](#)).

- Modified Strategy #2 to handle ICEs for primary endpoint will be modified as below:
 - Treatment discontinuation: a treatment policy strategy will be applied where all the observed values will be used regardless of the occurrence of the ICEs. Missing data due to any reason will be handled by using a multiple imputation with a copy-reference approach (see [Section 8.1.1](#)).
 - Use of a pre-defined prohibited medication in the week before any assessment of SANDE: a composite strategy will be applied where any data collected in the week after the occurrence of the ICE (if present) will be replaced by a value worse than all values observed for SANDE Global Score at week 8.

The modified strategy #1 will be analyzed as described for the primary estimand.

For the modified strategy #2, the following approach will be followed to combine the two different types of imputation and to prevent the bias related to the use of prohibited medications from spreading to all imputed values:

- Any datapoint collected in the week after intake of prohibited medications will be set to missing and imputed as done for any other missing data by using the copy-reference approach as described in [Section 8.1.1](#). In this way, all data can be imputed without letting the bias related to use of prohibited medications spread to other imputed values. Fifty datasets are obtained.
- Modified strategy #2 is applied in any dataset to data collected at Week 8: if the value for SANDE Global Score at Week 8 was observed (and then replaced by imputation in the previous step) in the week after an intake of a prohibited medication, this value is now replaced by the worst possible value (i.e. 100). In this way, the relationship among the variables inserted in the FCS regression is not affected by the replacement with the worst value.

Change from baseline at Week 8 is calculated and used in the ANCOVA model with the trimmed approach described by Permutt and Li (Permutt T and Feng L. 2017). Only Baseline value and Treatment are used as covariates. Fifty models are run, one for each imputed dataset. This method provides an exact test that does not require any modeling assumption. The estimand of the primary analysis is the difference between treatment groups in mean SANDE change from baseline to week 8 in the FAS population, including all patients who have no SANDE measurement at week 8 for any reason. The exact imputed value does not matter, as long as it is worse than all values observed in patients with SANDE measurements at week 8. The only requirement for this method is that it must be reasonable to consider the outcome of dropouts as worse than the highest SANDE Global Score of the completers. The estimand is the between-group difference in mean change from baseline in the percentage k subpopulation with the lowest SANDE values at Week 8. For this analysis, k=50%, 70%, and 90% will be used. The principle is to exclude all imputed data. Thus, if the missing rate is higher than 10%, k will be adjusted accordingly. The method is based on an exact permutation test for the null hypothesis that the treatment distributions for the considered outcome at week 8 are equal.

From each dataset, the observed mean difference between each active arm and the vehicle is derived. Then, a permutation distribution is calculated in order to derive the SE of each difference by using the permutation standard deviation. Finally, observed mean differences and their SEs are used to combine the results in the PROC MIANALYZE by using the Rubin's rule.

In case no data at Week 8 are collected after having taken a prohibited medication in the previous week, this sensitivity analysis is skipped.

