10 STATISTICS

10.1 SAMPLE SIZE

The sample size of the study is calculated based on results from the previous study NGF0118 using the subgroup of patients with baseline SANDE Global Score > 50. Expecting a mean difference of about 11 points (with unequal standard deviations in the active and vehicle groups: observed mean changes (SD) were -28.2 (26.36) and -17.4 (20.29) for IMP and vehicle, respectively) in improvement of SANDE Global Score from baseline to Week 8 in favor of rhNGF ophthalmic (eye drop) formulation, a total sample size of 276 evaluable patients (92 per group) is needed. This will allow to achieve an overall power of 80% for demonstrating superiority of at least one concentration of rhNGF ophthalmic formulation over vehicle in the improvement of SANDE Global Score from baseline to week 8, with an overall one-sided alpha of 0.025.

The sample size calculation takes into consideration a Bonferroni correction for two comparisons (2 concentration groups versus vehicle), i.e., the alpha level has been set to 0.0125 one-sided for each comparison.

Assuming a 5% rate of patients not evaluable for primary analysis after enrollment, the total number of patients to be enrolled in the study will be about 291 (97 per group). Enrollment will be competitive.

In Dompé previous studies, a screen failure rate of about 20% has been observed (NGF0121 - PROTEGO-1). This fact implies that approximately 350 subjects will need to be screened in order to have 291 patients enrolled and at least 276 evaluable. In any case, the screen procedures should be interrupted when the expected sample size of 291 subjects has been reached.

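### The trimmed-mean supportive analysis (SAP 8.1.3, modified strategy #2) is described as exact and free of imputed data, but the steps specified keep most imputed dropout values at k=90% and pool approximate results

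*SAP*

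**What the plan says.** SAP 8.1.3 defines modified strategy #2 in two parts. Treatment discontinuation is handled by treatment policy, and data missing for any reason are imputed by copy-reference. A SANDE score taken in the week after prohibited medication is handled by a composite strategy, as a bad outcome.

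The steps that implement this are:

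1. "Any datapoint collected in the week after intake of prohibited medications will be set to missing and imputed as done for any other missing data". This uses the copy-reference method of SAP 8.1.1 and yields 50 datasets.
2. In each dataset, a Week 8 score that had actually been observed in the week after prohibited medication is overwritten with 100. No other missing score is overwritten.
3. An ANCOVA with trimming is run in each dataset, keeping the best 50%, 70% and 90% by Week 8 SANDE.
4. A permutation SD is taken as the SE of each difference; then "observed mean differences and their SEs are used to combine the results in the PROC MIANALYZE" by Rubin's rule.

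The same section describes the method in other terms. It calls the test exact and free of modelling assumptions. It says the imputed value is immaterial provided it is worse than every observed Week 8 score. It adds a condition, in which the comparison is with completers: "The only requirement for this method is that it must be reasonable to consider the outcome of dropouts as worse than the highest SANDE". It states that "The principle is to exclude all imputed data", and for that reason says k will be adjusted if more than 10% of data are missing.

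Protocol 10.6.3 holds the root of the conflict: copy-reference for missing data, beside a trimmed method said to be exact and to need dropouts ranked worst. The exclusion rule, the adjustment of k and the Rubin pooling appear only in the SAP.

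**The concern.** A trimmed mean removes dropouts from the comparison only if they sit at the bad end of the ranking. Copy-reference scores do not sit there. SAP 8.1.1 says the approach limits the effect after discontinuation to that of vehicle, so imputed scores fall among the ordinary observed ones and many are kept after trimming.

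The inference has the same problem. A permutation p-value is exact because it is read from the permutation distribution. Taking only the SD of that distribution, using it as a standard error and pooling over 50 imputations gives an approximate result that depends on a regression fitted to the vehicle arm.

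At stake is the accuracy of the description. A programmer cannot satisfy both halves of the text, and a reader of the results would be told of properties that the analysis lacks.

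**Working it through.** **The plan's own figure.** The documents give no number for the trimmed analysis, so the check starts from the sample size, whose inputs are reused below. Protocol 10.1 gives: "observed mean changes (SD) were -28.2 (26.36) and -17.4 (20.29) for IMP and vehicle, respectively"; "the alpha level has been set to 0.0125 one-sided for each comparison"; target power 80%.

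- Difference: 28.2 − 17.4 = 10.8.
- SE at 92 per group: √((26.36² + 20.29²)/92) = √((694.85 + 411.68)/92) = 3.47.
- Ratio: 10.8/3.47 = 3.11. The Welch t calculation at one-sided 0.0125 gives power 80.2%, and 92 is the smallest n that reaches 80%.
- Loss of 5%: 92/0.95 = 96.8, so 97 per group and 291 in total.

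The plan's 92 and 97 are reproduced.

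**Where imputed scores fall.** One active arm and the vehicle arm were simulated with 97 patients each, 400 repetitions, and the mean changes and SDs above.

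- Assumed, because the documents do not give them: baseline mean 70, SD 12, restricted to 50–100; a change that depends modestly on baseline; 5%, 10% or 15% missing at Week 8, completely at random and equal in both arms.
- Missing scores were drawn from a regression on baseline fitted to observed vehicle patients, bounded 0–100 and rounded, as SAP 8.1.1 requires. Week 4, which the SAP also uses, was left out for simplicity.
- The best k% by Week 8 score was kept within each arm.

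The median imputed score was 52–53, against a highest observed score near 100. Only about 0.03% to 0.1% of imputed scores exceeded the highest observed one.

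**Share of imputed values surviving trimming:**

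| Handling of missing Week 8 scores | k=50% | k=70% | k=90% |
|---|---|---|---|
| Copy-reference, as specified (5–15% missing) | about 41% | about 63% | 88–89% |
| Ranked worst, 5% or 10% missing | 0% | 0% | 0% |
| Ranked worst, 15% missing | 0% | 0% | 33% |

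The 33% is simple counting. With 15 of 97 missing, 82 are observed; k=90% keeps 87, so 87 − 82 = 5 of the 15 missing patients are kept. That is the situation the sentence on adjusting k addresses, and it makes sense only under worst ranking.

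**In patients.** At the planned 5% loss, 0.05 × 291 = 14.6 patients are missing. About 14.6 × 0.89 = 13 imputed values stay in at k=90%, 14.6 × 0.63 = 9 at k=70% and 14.6 × 0.41 = 6 at k=50%.

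**The inference.** If every imputed Week 8 value really were trimmed, the 50 datasets would give essentially the same estimate and pooling would add nothing. Pooling has a purpose only because imputed values remain. The exclusion rule and the pooling step therefore cannot describe the same analysis.

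**The case against.** The strongest reply is that copy-reference for dropouts is deliberate. Both documents assign it to missing data under strategy #2, and the SAP says it is combining two kinds of imputation. On this view the steps are the plan and the method description is surplus text. That reading is fair, and it is why worst ranking is not the only remedy. It does not rescue the statements on exactness, exclusion of imputed data, dropouts being worst, or the adjustment of k, which remain untrue of those steps.

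A second reply is that little changes numerically. Under the same kind of assumptions, with 5% missing at random in both arms, copy-reference and worst ranking gave differences of −10.6 and −10.7 at k=90%, −12.3 and −12.6 at k=70%, and −13.8 and −14.2 at k=50%, against a sampling SD of about 3.3 to 3.7. This stands for small, balanced, random loss. It is weaker when loss is unequal. With 10% missing in the active arm and 5% in vehicle, the gap at k=70% was about 0.5 points. At k=90%, ranking 10 of 97 active patients worst uses all 97 − 87 = 10 trimmed places, so no poorly scoring active completer is trimmed, whereas in vehicle 5 of the 10 trimmed places still go to completers.

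A reader might also infer that this analysis was meant to show that the result does not depend on imputation, and now fails to. The documents do not say so. SAP 8.1.3 presents it as a change of estimand, in how prohibited medication is handled. Robustness to missing data is covered in SAP 8.1.2 by MAR imputation, the tipping point, complete cases and all observed cases. Nor is it right that trimming removes no imputed values: at k=50% more than half are removed.

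**Conclusion.** The inconsistency is real and lies within SAP 8.1.3, with its root also in Protocol 10.6.3. As specified, the analysis is approximate, depends on the vehicle-based imputation model, and keeps about 89%, 63% and 41% of imputed dropout values at k=90%, 70% and 50%. These shares rest on the assumed baseline distribution and random missingness, and average over the arms: about 90%, 70% and 50% in vehicle and about 87%, 59% and 33% in the active arm. The 5% used for patient counts is the planning rate for non-evaluable patients, not a known Week 8 missing rate. The direction does not rest on these assumptions, because vehicle-like scores lie inside the observed range.

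The problem concerns truly missing scores. Observed scores after prohibited medication do go to 100, although 100 can tie with an observed 100 and so is not strictly worse than every observed score.

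The importance is minor. The analysis is supportive, carries no alpha, and is skipped if no Week 8 score follows prohibited medication. A reader should not infer any fault in the primary test, its alpha or the sample size.

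**What to change.** Before database lock, choose one route and make SAP 8.1.3 consistent with it, noting the departure from Protocol 10.6.3.

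**(a) Follow the method description.** Rank every patient without a usable Week 8 SANDE (missing, or taken in the week after prohibited medication) worse than all others. Set k no larger than one minus the highest arm-specific share of such patients. Do no imputation, and take the p-value directly from one permutation distribution per comparison. The code becomes simpler, one run instead of 50. The cost is of substance: loss for any reason counts as failure, and the treatment-discontinuation bullet, which now prescribes copy-reference, must be rewritten. Protocol section 13 records that these supportive analyses were updated at FDA request, so the change should be documented as one of estimand.

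**(b) Follow the steps.** Keep copy-reference for missing scores and 100 for scores after prohibited medication. Delete the statements that the test is exact and model-free, that imputed data are excluded with k adjusted to that end, and that dropouts rank worst. Report the result as approximate and dependent on the imputation model. This costs only wording.

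Route (b) is the smaller change and keeps the missing-data strategy that both documents state. Route (a) is needed if an exact test free of imputation is wanted.
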